## 8.0 Blood Analysis

---

- 8.1 **Cytokines** (IL-6, IL-8, IL-10, IL-1 $\beta$ , IFN- $\gamma$ , & TNFr1) will be assessed in the blood at all five assessment time points. A fasting blood draw (minimum of 8 hours) will be performed on all participants at all five assessment time points. The standard URCC NCORP Research Base blood collection protocol will be used. Six tubes of blood (approximately 50ml) will be collected including: two red top tubes for serum, two purple top EDTA-heparin tubes (1 for plasma and 1 for DNA) and 2 Paxgene tubes for RNA. Cytokines will be analyzed and any remaining blood samples including serum, plasma and whole blood for DNA and RNA analyses will be used by [name] and members of her research team for additional exploratory analyses. The remaining blood samples are not banked or made available for use by investigators outside of [name] research team. All NCORPs will handle all human biological materials and disposal of biohazard waste in accordance with biosafety level II guidelines at their respective institutions for blood collection, handling, disposal, storage and shipping. All NCORP personnel handling human biological materials and laboratories used by NCORPs must have received appropriate biosafety certifications and meet routine inspection guidelines according to their facility guidelines.
- 8.1.1 All requisitions, blood tubes, microfuge tubes, freezer boxes, pipettes, and labels for blood draws are provided by the Research Base in the form of barcoded and pre-labeled patient kits. All patient kits are study specific.

**DO NOT MIX REQUISITIONS, BLOOD TUBES, MICROFUGE TUBES OR PIPETTES ACROSS PATIENT BLOOD DRAW KITS EVEN IN THE SAME STUDY BECAUSE THE BARCODES AND LABELS ARE KIT SPECIFIC.**

**DO NOT MIX THE FREEZER BOXES, LABELS OR EXTRA SUPPLIES PROVIDED ACROSS STUDIES EVEN URCC RESEARCH BASE STUDIES, BECAUSE THEY ARE STUDY SPECIFIC.**

All coordinators will fill in the appropriate patient information on the requisition form in each kit when it is assigned to the patient. Every time a patient blood draw is performed a separate new patient kit is used

and assigned to the study participant. Each NCORP is responsible for designating an individual that is certified and a lab or facility that meets the biosafety level II criteria to perform the blood draws and to handle, dispose, store and ship the blood samples appropriately. The individual designated to perform the blood draws, handle, dispose, store and ship the samples must participate in the training provided by the URCC NCORP Research Base, previously described in section 6.0, and be approved by the study PI (or PI's designee) prior to any blood collection at each NCORP site.

- 8.1.2 Serum will be extracted from the two red top tubes for estimation of cytokines (IL-6, IL-8, IL-10, IL-1 $\beta$ , IFN- $\gamma$ , & TNFr1). Plasma will be extracted from one of the purple top EDTA-heparin tubes for estimation of cytokines (IL-6, IL-8, IL-10, IL-1 $\beta$ , IFN- $\gamma$ , & TNFr1). To extract the serum and plasma, the tubes will first sit upright for 30 minutes at room temperature after blood collection. Second, the tubes will then be put into a centrifuge (note temp) and spun for 15 minutes at 1600 x g. After 15 minutes, there should be a clear separation of the serum or plasma (yellowish liquid on top) from the other cells. If this is not evident, then centrifuge for 15 additional minutes. The upper layer of serum (red top tubes) and plasma (purple top tube) is then gently aliquotted into the 2.0 ml microfuge tubes provided in each URCC NCORP patient blood draw kit. Serum from the red top blood tubes is to be placed into the pre-labeled pink microfuge tubes. Plasma from the purple top tube is to be placed in the pre-labeled purple microfuge tubes. All microfuge tubes are then placed in the pre-labeled freezer boxes provided by the URCC Research Base and the freezer box is then placed in either a -20 C or a -80 C degree freezer (-80 C is preferred if available but not required) for storage until shipped to URCC Research Base. Cytokines (IL-6, IL-8, IL-10, IL-1 $\beta$ , IFN- $\gamma$ , & TNFr1) will be assessed using Multiplex and ELISA methods as appropriate. The remaining serum and plasma will be stored, as part of study participation, for use in future research by [name], the study PI, and her research team at the URCC Research Base.
- 8.1.3 One purple top EDTA-heparin tube and two Paxgene tubes will be prepared and stored for future DNA and RNA extraction. The EDTA-heparin tube will be rocked 10 times and then placed upright in a -20 C freezer for a minimum of 24 hours. After 24 hours, the EDTA-heparin tube can then be transferred to a -80 C freezer if available. The two Paxgene tubes will be rocked 10 times, stored upright for minimum of 2 hours and a maximum of 24 hours at room temp and then placed upright in a -20 C freezer for a minimum of 72 hours. After 72 hours, the Paxgene tubes can be transferred to a -80 C freezer if available. After the tubes have been frozen upright for their designated time above, they can then be placed on their side in the pre-labeled freezer boxes provided by the Research Base. (Storage in a -80 C freezer after 4 days is preferred if available but not required.) The whole blood in these tubes will be stored, as part of study participation, for use in future research by [name], the study PI, and her research team at the URCC. See the Blood Procedures Manual found on the URCC Research Base website for complete blood processing instructions.
- 8.1.4 **Shipping Supplies to NCORPs and Inventory Tracking:** Upon notification of the Research Base that a NCORP has registered a cohort for this study, a starter blood drawing package and an initial supply of barcoded and pre-labeled blood draw kits will be shipped to the NCORP for distribution and use.

Each NCORP site will be responsible for designating someone on the research staff to be responsible for receiving the blood draw supplies and kits. The staff member will verify that the shipment contains the correct number of supplies and kits and that the supplies and kits are in good condition. The identification numbers need to be verified for accuracy and recorded. The Investigational Device Accountability Record (DARF) will be used to track supplies and kits arriving from the Research Base, kits given to participants, samples stored, and samples shipped to the URCC NCORP Research Base.

8.1.5 **Shipping Frozen Blood Samples to URCC Research Base:**

**PRIOR TO SHIPPING SAMPLES, YOU MUST CONTACT THE URCC RESEARCH BASE TO MAKE ARRANGEMENTS TO RECEIVE YOUR SAMPLES.**

Call:  
[name]  
[contact]

Ship Samples To:  
ATTN: [name]  
University of Rochester Medical Center  
Wilmot Cancer Institute, PEAK Laboratory (B-5035)  
[name]  
[name]

Samples are to be stored in URCC-supplied freezer boxes as outlined in the Blood Procedures Manual found on the URCC Research Base website. Samples must be stored at a minimum of -20C, but preferably at -80C. Samples cannot be stored at -20C for longer than 3 months.

The NCORPs are responsible for shipping all samples to the Research Base within 3 months of sample collection. All samples must be shipped priority overnight and frozen on dry ice. Each NCORP is responsible for adhering to Federal Guidelines for shipping biosafety level II biohazards as well as URCC NCORP Research Base biosafety level II guidelines (outlined in the blood procedures manual provided), their NCORP institutional biosafety level II guidelines and the shipping company guidelines when packing and shipping the frozen blood samples to the Research Base.

---

## 9.0 Design Consideration

---

- 9.1 **Decision to conduct a trial comparing YOCAS® to a gold standard insomnia treatment for the general population:** We considered proposing a dismantling trial to determine which component of YOCAS® is the most active. However, after much deliberation with colleagues, we believe the study comparing YOCAS® to CBT-I has significantly greater potential to impact standard of care for insomnia among cancer survivors and, potentially, other populations.
- 9.2 **Changes From Our Prior Yoga RCT:** In this study, we extend our previous findings by comparing YOCAS® to CBT-I (a gold-standard treatment for insomnia in the general population) and a health education intervention controlling for time and attention. We also blind study participants to control for demand characteristics and bias. We provide participants with “Yoga Kits,” including mat, strap, Subject DVD, and manual to facilitate home practice during the intervention period and sustained practice during the following 6 months and assess the durability of intervention benefits at 3 and 6 months following completion of the interventions. We add assessments of cardiopulmonary function, muscular function and inflammation to test the direct effects of yoga on these outcomes and their mediational effects on insomnia through YOCAS®.
- 9.3 **Length of Intervention—Why 4 and 8 Weeks:** We used a 4-week intervention period for YOCAS® in our first study for two main reasons: 1) 4 weeks was the minimum length, in the published literature, shown to be efficacious for improving sleep problems, and 2) for practical purposes, we felt this length was reasonable for implementation in community settings via private oncology practices and would have good adherence. We have chosen to retain the 4-week period for YOCAS® as it was previously shown to be effective and to compare it to CBT-I delivered over the gold-standard 8-week period. We are aware that new versions of brief and electronic CBT-I are currently being evaluated for efficacy among survivors, but we feel it is important to use the form of CBT-I shown to be effective among groups of cancer survivors in published literature.

- 9.4 **Length of Follow-Up—Why 3 and 6 Months:** We chose 3- and 6-month follow-up assessments because they will provide good information on the short and longer-term benefits of the yoga intervention, and, while clearly reflective of long-term influence, a 12-month follow-up is not practical within the time period of this R01-funded project.
- 9.5 **Decision to Conduct a Multicenter Study:** It is not possible to recruit the necessary 720 cancer survivors at a single location within the 5-year time period of an R01. We have considerable experience successfully conducting large, multicenter phase III RCTs through the Research Base with our NCORP affiliates—accrual of the required 720 participants in this environment is possible, and our previous studies demonstrate that it is highly probable they will be successfully accrued within the timeframe of this R01-funded project.

---

## 10.0 Data Handling and Statistical Considerations

---

- 10.1 **Sample Size and Statistical Power:** Allowing for 30% of participants who may not provide complete data (as in our prior study), we will need to enroll a total of 720 participants to have 504 fully evaluable participants (168 evaluable in each of the three study arms). Fully evaluable participants is defined as having completed the On Study/ Participant Interview and the Clinical Record Information (baseline), the ISI, PSQI, Daily Diaries, and actigraphy (baseline and post-intervention assessments) for primary and secondary endpoints. With 504 fully evaluable participants, will have 80% power at a 0.025 significance level to test our hypotheses. We will use a significance level of 0.025 to control for type I error because two hypotheses (i.e., 1 inferiority [yoga vs. CBT-I] and 1 superiority [yoga vs. health education]) will be tested in our primary aim. *[Note: We will reimburse survivors for participating in this study in an effort to decrease attrition and data loss.]*
- 10.2 **Power for Primary Aim 1:** The two primary hypotheses to be tested in our primary aim include: (1) YOCAS® will be as effective as CBT-I, and (2) YOCAS® will be more effective than the health education control.
- 10.2.1 **Power for Hypothesis 1:** Based on baseline data from our previous phase III RCT examining the effects of yoga on insomnia and data from Savard and Morin, we assume an ISI standard deviation of 4.6. Since half a standard deviation is commonly accepted as appropriate for estimating a clinically important change, we regard a difference of 2.3 (half a standard deviation) between YOCAS® and CBT-I as nontrivial. Following the same methods as Garland and colleagues, we set the non-inferiority margin to 1.15 (half of the 2.3 difference). We will test the **null** hypothesis that the difference in mean change on the ISI between YOCAS® and CBT-I is greater than 1.15; that is, YOCAS® is *inferior* to CBT-I. Rejection of the null hypothesis means that YOCAS® is as effective (*non-inferior*) as CBT-I. Using ANCOVA to estimate differences in mean change between YOCAS® and CBT-I, a correlation of 0.576 (from our prior study), and a sample of 168 subjects per group, we will have sufficient (80%) power to detect non-inferiority using a margin of 1.15 at  $p = 0.025$ .
- 10.2.2 **Power for Hypothesis 2:** Using ANCOVA to estimate differences in mean change between YOCAS® and health education, a correlation of 0.576 (from our prior study), and a sample size of 168 evaluable subjects per group, we will have sufficient power to detect differences on the ISI of at least 1.3, 1.5 and 1.6 (all larger than our 1.15 non-inferiority margin) at 80%, 90%, and 95% power, respectively. (Note: It is already well-established that CBT-I is superior to general health education and equal time and attention, as such an overall test of group differences is not necessary or sufficient—the differences in question are specifically between yoga and CBT-I and yoga and health education and require two separate hypotheses be tested.)
- 10.3 **Study Timeline:** Based on our prior experience conducting studies in the URCC Research Base, we anticipate that study start-up activities (e.g., obtaining NCI and IRB approvals, presenting the protocol and training NCORP site staff, setting up databases, registration and randomization, ordering supplies and making kits and manuals, sending kits and other study supplies to NCORPs) will take approximately 6 months. Screening and accruals will

begin during the 7th month and continue through month 54. The final 6 months will be used to retrieve any remaining data, supplies and equipment from NCORPs, to conduct final audits of the data, to conduct analyses, to write abstracts and papers, and to present findings at meetings. We expect it will take between 24 and 47 months to accrue the 720 participants needed for this study.

- 10.4 **Representation of Women and Minorities:** None of the eligibility criteria for the study involve gender or ethnicity. Past enrollment in our NCORP studies has closely paralleled the gender and ethnic composition of the available population. See section 12.0 on Gender and Minorities.
- 10.5 The same **protocols and procedures for data quality and control** that we have used for our previous URCC Research Base protocols will be used for this study. Data will be entered on scannable forms (Teleform) and electronically sent to a Microsoft Access database. After scanning, data are audited visually for errors, and then the entire database is re-audited. MPlus, R and SAS statistical packages will be used for the analyses.
- 10.6 Unless otherwise stated, all statistical tests will be performed at the two-tailed 5% level of significance. Likewise, 95% confidence intervals will be constructed for estimation of effects (e.g., difference in mean CRF, aerobic capacity, strength and QOL between the active treatment group and the control group). Data will be analyzed on an "intent-to-treat" basis; participant data will be included in the treatment group to which the participant was randomized, regardless of any subsequent changes to the treatment (treatment in this study is considered the study intervention, i.e., exercise intervention, CBT-I, or Health education standard care).
- 10.6.1 **Assumptions.** The assumptions underlying all statistical analyses will be thoroughly checked using appropriate graphical and numerical methods. For the ANCOVA analyses, the assumptions are bivariate normality of the Pre- and Post-treatment responses with common covariance matrices, after correction for the model fixed effects. Bivariate normality will be assessed with Roysten's procedure, and equality of the covariance matrices will be assessed with the Box M test. The ISI data from our previous trial did not show violations of these assumptions. If distributions are markedly skewed, we will apply transformations as appropriate. The biomarker data will likely require a logarithmic transformation, as is common practice. If heteroscedistic variance is found in the residuals for any of the models, a Box-Cox transformation will be applied to the data. As a last resort, appropriate nonparametric methods will be attempted, e.g. Wilcoxon rank sum test on change scores. If outliers or influential data are detected, the accuracy of the data will be investigated. If no errors are found, analyses may be repeated after removing these cases to evaluate their impact on the results. However, the final analyses will include these data points.
- 10.6.2 **Missing Values.** Every effort will be made to facilitate participants' completion of questionnaires and provision of actigraphy and physical function data, and blood. In the event of missing data, the reasons for missing data will be recorded and tabulated according to treatment group. Some missing data are inevitable. Under the missing at random (MAR) assumption, we will use multiple imputation to obtain unbiased estimates of key parameters. If data are suspected to be missing not at random (MNAR), a sensitivity analysis using the methods of Liublinska and Rubin (2014) will be run to determine the impact on results. If the estimates are similar to the ones obtained from the simpler analysis of only complete cases, we will report the complete-case analysis results.
- 10.7 **Statistical Analyses:**
- 10.7.1 **Primary Aim 1 Analyses:** To determine if YOCAS® is as effective as CBT-I and more effective than health education for improving **insomnia (ISI total)**, two separate analyses will be performed, each aimed at estimating the difference between arms in mean change from baseline with associated confidence intervals. The comparison of YOCAS® to CBT-I is a non-inferiority hypothesis with a one-sided alpha, and the comparison of YOCAS® to the health education control is a traditional null hypothesis of no difference with a two-sided alpha. See the Statistical Power section for more details. A linear mixed effects ANCOVA will be used to assess the statistical significance of the differences in mean changes from baseline for the two groups (Hypothesis 1 = YOCAS® vs. CBT-I;

Hypothesis 2 = YOCAS® vs. health education). **The response will be post-treatment ISI total score.** The model fixed effects will be Group and Baseline ISI. NCORP Site will be included as a random effect. The REML method will be used to estimate the random effect variance components. If the NCORP Site variance component is significant, the fixed effects will be tested using F tests with the Kenward-Roger degrees of freedom adjustment. If the NCORP Site variance component is not statistically significant, we will use ordinary least-squares estimation and F-Tests for testing the fixed effects. The mean difference between groups with associated 95% confidence intervals will be estimated using the appropriate contrasts. An alpha level of 0.025 will be used to adjust for multiple comparisons. Additional follow-up analyses will include NCORP site and cohort as covariates and examine possible interactions.

- 10.7.2 **Secondary Aim 2 Analyses:** To examine if YOCAS® is effective for improving **objective symptoms of insomnia** (sleep latency, sleep efficiency, wake after sleep onset, sleep duration, and daytime napping via actigraphy) and **global sleep quality impairment** (PSQI total) compared to CBT-I and a health education control, we will use the same methods as for Primary Aim 1 with no multiple comparison adjustments.
- 10.7.3 **Secondary Aim 3 Analyses:** To examine if YOCAS® and CBT-I are effective for **maintaining improvements in insomnia at 3 and 6 months post-intervention** compared to a health education control, we will perform a longitudinal analysis using the ISI total score at all five time points as the response. The fixed effects will be Time, Group (all three in this analysis), and Time by Group interaction. Within-subject random effects will initially be modeled assuming an unstructured covariance matrix, but will be simplified after inspection of the estimated covariance structure (e.g., compound symmetry). If NCORP Site variance in the primary analysis is statistically significant at the 0.05 level, it will be included as an additional random effect, independent of the within-subject random effects. REML estimation will be used. Fixed effects will be tested using F tests with the Kenward-Roger degrees of freedom adjustment. The impact of group on the time trajectory of insomnia will be tested via the Time\*Group interaction. Least-squares means for each Time and Group combination will be plotted to visualize and understand the time trajectories of insomnia. Differences in time trajectories between the three groups will be tested with no adjustments for multiple comparisons.
- 10.7.4 **Exploratory Mechanistic Aim 4 Analyses:** To explore whether YOCAS® is effective for improving **circadian activity rhythms (24 and 12 hour amplitudes and acrophases via actigraphy), physical function (i.e., cardiopulmonary [6-min. walk] and muscular function [dynamometry]), and inflammation (IL-6, IL-8, IL-10, IL-1 $\beta$ , IFN- $\gamma$ , & TNFR1 via standardized ELISAs and multiplexes)** compared to CBT-I and a health education control, we will use the same analytical methods as for Primary Aim 1 to assess changes in the estimated parameters of the two-oscillator (12 and 24 hours) cosinor model and the Hill function model. These parameters include **Mesor (M), Amplitude (A1) and Acrophase (Phi1) for the 24-hour oscillator and Amplitude (A2) and Acrophase (Phi2) for the 12-hour oscillator.** Estimates will be from the log-transformed activity counts using nonlinear regression. Degree of rhythmicity will be assessed with the Fisher-transformed model multiple correlation. We will also fit single-oscillator models (24-hour Mesor, Amplitude, and Acrophase) for comparison with other published studies. The time participants woke up in the morning and fell asleep in the evening will be extracted from weekly diaries. We will apply the same methods as for physical function and inflammation outcomes; inflammatory biomarkers will be log-transformed as needed.
- 10.7.5 **Exploratory Mechanistic Aim 5 Analyses:** To explore **whether changes in physical function, circadian rhythm and inflammation mediate the effect of YOCAS® on insomnia,** we will use separate mediation analyses performed on pre-post ISI change scores (CS) and the above outcomes as potential mediators. Path analysis will be used, where the intervention affects CS, the intervention affects the mediator, and the mediator, in turn, affects the CS. We will also use structural equation modeling. Mediation will be assessed via indirect effect estimation using bootstrap-based 95% confidence intervals. Latent variables will be introduced into the model for multiple measures of a common entity (e.g., cytokines for inflammation). If multiple measures are weakly correlated, we will split them

into separate measurement terms (e.g., pro- and anti-inflammatory cytokines). MPlus software will be used, with full-information maximum likelihood (FIML) estimation. Under MAR, this provides less biased estimates due to missing data.

10.7.6 **Additional Analyses:** The following analyses will be interpreted cautiously for hypothesis generation. We will use the same analytical methods described for Aims 2, 3, 4 and 5 to explore the interrelationships between insomnia, SQI, sleep chronotype, CRF, depression, anxiety, mood, hormone therapy, pain, cognitive problems, symptoms, exercise, cardiopulmonary function, strength, inflammation, stimulant and sleep medication use.

10.7.7 **Interim Analyses:** No interim analyses of efficacy data from the trial are planned.

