- 6.9 All instructors will complete an Attendance Log for each session to assist in documenting intervention compliance by instructors and participants. They will return these logs to the study coordinator. The Coordinator will darken the participants names; leaving only the initials visible. They will in turn submit attendance logs for each of the three study arms to the Research Base. One attendance log is to be submitted at the end of the intervention for each intervention session for all 3 study arms. The names should be darkened to leave just participant initials visible.
- 6.10 **Coordinator Training:** All NCORP coordinators and staff must complete mandatory training conducted by Research Base staff and PEAK Lab staff for this study. The training includes study orientation, actigraphy, handgrip testing, 6-minute walk test, and blood drawing, processing, storage and shipping. The training lasts approximately 2 hours.

- 6.11 **Screening:** Cancer survivors 2-60 months post-primary (i.e., surgery, chemotherapy, radiation) treatments, who have been treated at NCORP communities affiliated with the URCC NCORP Research Base will be screened. A screening consent form will be used by the coordinators when approaching potential study participants either over the phone or face to face. If the person declines participation in the study, the screening consent form will be destroyed. If the person agrees to discuss the study, a screening consent form will be completed and submitted to the Research Base. At screening, the DSM-V and ISI screening forms will be used to determine eligibility for the study. All persons presented with this study will be entered on a REDCap screening log found on the Research Base website.

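### The YOCAS versus CBT-I non-inferiority test has no adherence-based supporting analysis, although non-attendance in CBT-I, or at similar rates in both arms, would favour non-inferiority

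*Combined protocol and SAP*

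**What the plan says.** Section 10.6 sets the analysis principle for the whole trial: "participant data will be included in the treatment group to which the participant was randomized, regardless of any subsequent changes to the treatment". Section 10.7.1 says that the YOCAS versus CBT-I comparison "is a non-inferiority hypothesis with a one-sided alpha", while YOCAS versus health education is a two-sided test of no difference. The margin comes from Section 10.2.1: "we set the non-inferiority margin to 1.15 (half of the 2.3 difference"). That section reads rejection of the null as showing YOCAS to be as effective as CBT-I.

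Two other analysis sets appear. Section 10.1 defines fully evaluable participants by completed forms, diaries and actigraphy. Section 10.6.2 allows a complete-case result to be the one reported when it resembles the imputed result. Both are defined by data completeness. A participant who attends one session but returns everything belongs to both.

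Adherence is recorded. Section 6.9 states: "All instructors will complete an Attendance Log for each session", and Section 6.16 adds diaries and actigraphy as adherence monitoring. The only further primary-aim analyses in Section 10.7.1 concern site and cohort. No section defines a minimum attendance or uses attendance in the test of Hypothesis 1.

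**The concern.** In a superiority comparison, participants who receive little of their assigned treatment usually pull the difference toward zero and so against the claim. In a non-inferiority comparison, a difference pulled toward zero supports the claim. The plan applies one rule to both hypotheses without comment.

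The conclusion at stake is that YOCAS can stand beside CBT-I as a gold-standard option (Sections 1.0 and 2.0). Many readers would take that as a statement about the two therapies when they are actually received. If CBT-I were poorly attended, or both arms similarly so, the trial could meet the margin partly because of the non-attendance, and no planned analysis of Hypothesis 1 would show it.

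**Working it through.** **Inputs from the documents.** Section 10.2.1: "we assume an ISI standard deviation of 4.6"; "a correlation of 0.576 (from our prior study), and a sample of 168 subjects per group"; margin 1.15. Section 10.1: "We will use a significance level of 0.025 to control for type I error because two hypotheses" are tested. Section 10.7.1: one-sided test.

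**The plan's own figure.** Section 10.2.1 states: "we will have sufficient (80%) power to detect non-inferiority using a margin of 1.15 at" the 0.025 level.

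- ANCOVA residual SD = 4.6 × √(1 − 0.576²) = 3.760.
- n per arm = 2 × [3.760 × (1.960 + 0.842) / 1.15]² = 167.8, so 168.
- SE of the difference = 3.760 × √(2/168) = 0.410.
- Power at true equality = Φ(1.15/0.410 − 1.96) = 80.0%.
- 168 / 0.7 = 240 per arm, 720 in total.

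The plan's figures reproduce.

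**Model for non-attendance (assumed).** Let E be the CBT-I benefit under full attendance, and let YOCAS be worse by exactly the margin, so its benefit is E − 1.15. Let qC and qY be the shares of effect lost to non-attendance in CBT-I and YOCAS. The as-randomised deficit is

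D = (1 − qC)·E − (1 − qY)·(E − 1.15) = 1.15 − qC·E + qY·(E − 1.15),

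and P(declare non-inferiority) = Φ((1.15 − D)/0.410 − 1.96). With no loss this is 2.5%.

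**Equal loss in both arms.** D = 1.15 × (1 − q), whatever the value of E.

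| q in both arms | D | P(declare non-inferiority) |
|---|---|---|
| 10% | 1.035 | 4.7% |
| 20% | 0.92 | 8.1% |
| 30% | 0.805 | 13.2% |

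**Loss of 20% in one arm only.** The documents do not give E, so it is varied from 2.3 to 8 ISI points.

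| E | CBT-I only: D | P | YOCAS only: D | P |
|---|---|---|---|---|
| 2.3 | 0.69 | 20% | 1.38 | 0.6% |
| 4 | 0.35 | 50% | 1.72 | 0.04% |
| 6 | −0.05 | 83% | 2.12 | about 0.001% |
| 8 | −0.45 | 97% | 2.52 | below 0.001% |

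**Where the direction turns.** D falls below 1.15 only when qC/qY > (E − 1.15)/E, which is 0.50, 0.71, 0.81 and 0.86 for E = 2.3, 4, 6 and 8. Above that ratio non-attendance favours non-inferiority; below it, non-attendance works against it. If the treatments were truly equal and YOCAS alone lost 20%, then at E = 4 the deficit would be 0.2 × 4 = 0.8, and power would drop from 80% to about 13%.

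The calculations assume effect proportional to attendance, an unchanged SD and a normal approximation, and they ignore site and group clustering.

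**The case against.** **The planned test is valid for what it tests.** The stated null concerns the difference in mean change between arms, participants are analysed as randomised, and the trial is described as comparing effectiveness. For that as-randomised effect the test keeps its 2.5% level. This stands. A reader might infer that the planned type I error is inflated; it is not. The 4.7% to 13.2% figures belong to a full-attendance hypothesis that the protocol does not state. The gap remains because the protocol does not say which effect its conclusion of equal effectiveness describes.

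**Direction.** A reader might also infer that non-attendance in either arm helps the claim. The YOCAS-only column above shows the opposite. This objection also stands.

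**Evidence.** The only attendance figure in the documents is for yoga: an average of 6.5 of 8 sessions in the prior trial (Section 2.0, Study 1). Reading the 18.75% missed as equal loss in both arms would give 7.6%, but nothing supports carrying it over to CBT-I, and missed sessions do not mean 18.75% of participants were untreated. The same account reports yoga practice averaging 182 minutes a week against 2 × 75 = 150 prescribed, and Section 9.2 adds kits for home practice. Class attendance is therefore an imperfect measure of yoga dose.

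**The third arm.** Hypothesis 2 and the longitudinal analysis in Section 10.7.3 both use the health education control, so a badly diluted CBT-I arm would probably show against it. That is a partial safeguard. It does not estimate the YOCAS versus CBT-I difference among those who attended.

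**Conclusion.** The concern holds in limited form. The plan names only an as-randomised analysis for Hypothesis 1, with a possible complete-case report that does not address attendance. Describing it as intent-to-treat and nothing else would overlook that complete-case provision.

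Non-attendance in CBT-I, or at similar rates in both arms, would move the result toward non-inferiority. With equal loss of 10% to 30% and a full-attendance deficit at the margin, the chance of declaring non-inferiority rises from 2.5% to between 4.7% and 13.2%. Loss concentrated in CBT-I could raise it much further, by an amount that depends on the unstated CBT-I benefit. Loss mainly in YOCAS would work against the claim and cost power.

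The documents do not show which attendance pattern will occur. That uncertainty is the reason to plan the check in advance. It does not make the intent-to-treat analysis wrong or call for replacing it.

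**What to change.** Keep intent-to-treat primary for both hypotheses, and state in Section 10.6 or 10.7.1 that it estimates the as-randomised effect. For Hypothesis 1, add to Section 10.7.1:

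- attendance tabulated by arm from the Attendance Log;
- one supportive adherence-based analysis, per-protocol or adherence-adjusted, with the attendance threshold fixed before results are seen, the same ANCOVA and the 1.15 margin;
- its estimate and confidence interval reported beside the intent-to-treat result;
- a rule that the equal-effectiveness conclusion is qualified if the supportive point estimate moves materially toward YOCAS being worse, for example beyond 1.15.

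The cost is SAP wording and one more model on data already collected, with the 168 per arm unchanged. The supportive set is smaller, is not protected by randomisation, and misses home practice. It should not become a second required test. If it had to meet the margin, power at true equality would be about 71% with 80% retained (n = 134 per arm: Φ(1.15/[3.760 × √(2/134)] − 1.96)) and about 65% with 70% retained (n = 118).
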